7.7.2 Laboratory Evaluations

Clinical laboratory events will be expressed in SI units. Out-of-reference-range values will be flagged as high (H) or low (L) in the listings. For analysis purposes, values preceded by a "<" or a ">"sign (i.e. those below or above the limits of quantification) will be considered equal to the lower or upper limit of quantification, respectively. Appendix VIII contains the laboratory parameters.

Summary data for each laboratory parameter will be presented for each continuous clinical laboratory parameter (including hematology, serum chemistry, coagulation, liver function test, and thyroid test). Descriptive statistics will be generated for actual values, change from baseline, and percent change from baseline.

A shift table of laboratory parameters of the baseline category to the worst post-baseline category will be based upon the upper or lower limits of the normal range. All out-of-range outside the normal ranges will be presented in patient listings.

Event of Special Interest: Liver Function Evaluations (LFTs)

The following summaries will be generated for LFTs:

- Boxplots displaying the distribution of the ratio of result/ULN at each scheduled visit by treatment group.
- Plots of concurrent and non-concurrent peak bilirubin versus peak ALT or AST will be presented by treatment group.
- Shift tables will also be employed displaying categorical shifts from baseline to maximum post-baseline category (collected using all scheduled and unscheduled visits) for each LFT parameter by treatment group. Categories for shift table are \leq ULN, > ULN to \leq 3 x ULN, \geq 3×ULN to \leq 5 x ULN, > 5 x ULN to \leq 10 x ULN, > 10 x ULN to \leq 20 x ULN
- Frequency (percentage) of patients with elevations of LFTs across various ULN categories:
 - ALT > 3xULN, >5xULN, >10xULN, >20xULN
 - o AST >3xULN, >5xULN, >10xULN, >20xULN
 - ALT or AST >3xULN, >5xULN, >10xULN, >20xULN
 - o Total bilirubin >2xULN
 - o ALT or AST >3xULN and total bilirubin >2xULN
 - ALT or AST >3xULN, total bilirubin >1.5xULN, and ALP <2xULN
 - ALT or AST >3xULN, total bilirubin >2xULN, and ALP <2xULN

In addition, a separate listing of LFT values outside the normal range will be listed separately.

7.7.3 Ophthalmologic Examination

An ophthalmic exam will be conducted in addition to a slit lamp examination. For each eye and eye structure (iris, conjunctiva, anterior chamber, cornea, lens, and lid), the frequency (percentage) of patients reporting Normal, Abnormal (not clinically significant [NCS]), Abnormal (clinically significant [CS]) results will be presented. An overall frequency of the change in status from baseline (unchanged, worsened, improved) will be summarized by treatment group and visit.

A per patient listing of the results of the ophthalmic exam at any visits with an overall assessment of abnormal, clinically significant result will be generated.

7.7.4 Vital Signs, Body Weight and BMI

Descriptive statistics will be provided for all vital signs including blood pressure (Systolic (mmHg), Diastolic (mmHg), pulse rate (bpm), oral body temperature, respiration rate (breaths/min), weight (kg), and BMI (kg/m²).

Change from baseline in vital signs will be summarized by visit and treatment group using descriptive statistics.

An outlier analysis of vital signs will be performed to summarize the frequency (associated percentage) of abnormal values at post-baseline visits (scheduled or unscheduled) by treatment groups for the following parameters (Temperature, Pulse, Systolic Blood Pressure, Diastolic Blood Pressure).

7.7.5 Electrocardiograms

ECG parameters, including ventricular rate, PR interval, QRS duration, max QRS amplitude, QT interval will be collected at each visit. ECG parameters for Bazett corrected QT (QTcB) interval [calculated: QT x (Heart Rate/60)^{1/3} msec] and Fridericia corrected QT (QTcF) interval [calculated; QT x (Heart Rate/60)^{1/2}msec] will be derived for each visit. Overall categorical assessments including rhythm, electrical pacing present in ECG, ST or T-wave changes, A-V Block, Ventricular Conduction defect, Infarct pattern/poor r-wave progression and overall ECG interpretation is collected at each visit.

Descriptive statistics will be used to summarize continuous parameters by visit and treatment group.

Frequency (associated percentage) of each of the overall categorical assessments will be summarized as well by visit and treatment group. A separate per patient listing will be generated displaying all ECG values for any patient with an overall interpretation on ECG classified as Abnormal, Clinically Significant.

An outlier analysis will be performed to summarize the frequency (associated percentage) of abnormal values at post-baseline visits (scheduled or unscheduled) by treatment groups for the following parameters (QTc, QTcB, QTcF, PR, QRS and HR).

The ECG measurements and changes from baseline as well as investigator assessment and interpretation will be provided in a data listing.

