7.5.4. Electrocardiogram (ECG)

Standard computerized 12-lead ECG recordings will be obtained. Each lead shall be recorded for at least 3 beats at a speed of 25 mm/sec. Triplicate recordings will be obtained prior to

dosing. The electrophysiological parameters assessed will be rhythm, ventricular rate, PR interval, QRS duration, QT interval, ST and T waves, Bazett-corrected QT interval (QTcB) and Fredericia-corrected QT interval (QTcF).

When an ECG is scheduled at the same time as blood draws, the blood draws will be obtained at the scheduled time points and the ECG will be obtained prior to the scheduled blood draw.

The Investigator or designee is responsible for reviewing the ECGs to assess whether the results have changed since the Screening/Baseline visit and to determine the clinical significance of the results. These assessments will be recorded on the CRF. For any clinically significant changes from Screening/Baseline (e.g., ischemic ECG changes, wave/interval changes, or arrhythmia), the Investigator must contact the CRO Medical Monitor to discuss continued participation of the patient in the study.

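### SAP 7.7.5 gives the Bazett exponent to Fridericia and the Fridericia exponent to Bazett, so derived QTcB and QTcF would each be reported under the other's name

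*SAP*

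**What the plan says.** SAP section 7.7.5 (Electrocardiograms) lists ventricular rate and QT among the collected parameters, and treats the corrected intervals as derived variables. The two derivation rules are:

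- "Bazett corrected QT (QTcB) interval [calculated: QT x (Heart Rate/60)^{1/3} msec"
- "Fridericia corrected QT (QTcF) interval [calculated; QT x (Heart Rate/60)^{1/2}msec"

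The section states that these values "will be derived for each visit". It then uses them in three ways:

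- In summary tables: "Descriptive statistics will be used to summarize continuous parameters by visit and treatment group".
- In an outlier analysis of post-baseline values "for the following parameters (QTc, QTcB, QTcF, PR, QRS and HR", with no numerical cut-offs given.
- In the ECG listings of measurements and changes from baseline.

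The protocol, in section 7.5.4 and in the ECG footnote to the schedule of assessments, names both corrections ("Bazett-corrected QT interval (QTcB) and Fredericia-corrected QT interval (QTcF" in section 7.5.4) but gives no formula for either. The two brackets in SAP 7.7.5 are therefore the only derivation rule in the documents.

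**The concern.** Bazett and Fridericia are named methods with fixed definitions. Bazett divides QT by the square root of the RR interval, and Fridericia divides it by the cube root. The SAP attaches the cube root to Bazett and the square root to Fridericia.

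A programmer who follows the SAP would produce mislabelled variables. One who uses the standard formulas would depart from the SAP. Either way, specification and output cannot both be right.

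The labels matter because the two corrections behave differently away from 60 bpm. The square-root correction gives larger values than the cube-root correction at faster rates and smaller values at slower rates. A reader of a table headed QTcF expects cube-root values. Above 60 bpm that table would show intervals that are too long and could show outliers that are not Fridericia outliers. Below 60 bpm it would understate the interval. The table headed QTcB would err in the opposite direction. Protocol section 1.1.2.2 describes conduction defects and arrhythmias as part of this disease, so the ECG safety tables are likely to be read closely.

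**Working it through.** **Inputs.** The two formulas come from SAP 7.7.5. The standard definitions are those of the two named methods. The QT values (400 and 380 ms), the heart rates and the 450 ms cut-off are assumptions for illustration; the documents give none of them.

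**Step 1: standard definitions in the SAP's notation.** With RR = 60/HR in seconds:

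- Bazett: QT / RR^(1/2) = QT × (HR/60)^(1/2)
- Fridericia: QT / RR^(1/3) = QT × (HR/60)^(1/3)

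**Step 2: SAP formulas as written, QT 400 ms and HR 80 bpm.**

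- SAP QTcB = 400 × (80/60)^(1/3) = 440.3 ms
- SAP QTcF = 400 × (80/60)^(1/2) = 461.9 ms

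**Step 3: standard formulas, same inputs.**

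- Bazett = 400 × (80/60)^(1/2) = 461.9 ms
- Fridericia = 400 × (80/60)^(1/3) = 440.3 ms

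The SAP's QTcB is the Fridericia value, and its QTcF is the Bazett value.

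**Step 4: across heart rates, QT 400 ms.**

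| HR (bpm) | True QTcF (ms) | Value the SAP labels QTcF (ms) | Error (ms) |
|---|---|---|---|
| 50 | 376.4 | 365.1 | −11.3 |
| 60 | 400.0 | 400.0 | 0.0 |
| 70 | 421.1 | 432.0 | +11.0 |
| 80 | 440.3 | 461.9 | +21.6 |
| 90 | 457.9 | 489.9 | +32.0 |
| 100 | 474.3 | 516.4 | +42.1 |

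Errors are taken before rounding. For QTcB, exchange the two value columns and reverse the signs.

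**Step 5: relative size, independent of QT.** The ratio of the SAP's QTcF to the true QTcF is (HR/60)^(1/2 − 1/3) = (HR/60)^(1/6). That is about 4% too high at 75 bpm, 7% at 90 and 11% at 110, and about 3% too low at 50. At QT 380 ms the corresponding values (true QTcF, then SAP QTcF) are:

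- 75 bpm: 409.3 and 424.9 ms
- 90 bpm: 435.0 and 465.4 ms
- 110 bpm: 465.1 and 514.5 ms
- 50 bpm: 357.6 and 346.9 ms

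**Step 6: effect on an outlier count.** Assume a 450 ms cut-off and HR 80 bpm.

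- The square-root value reaches 450 ms at an uncorrected QT of 450 / (80/60)^(1/2) = 389.7 ms.
- The cube-root value reaches it at 450 / (80/60)^(1/3) = 408.9 ms.

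A patient with QT between these two values is a Bazett outlier but not a Fridericia outlier. Under the SAP that patient would be counted as a QTcF outlier and not as a QTcB outlier.

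**The case against.** The exchange of exponents is hard to dispute. Both brackets are complete and legible, and a text-extraction fault would have had to swap two separate exponents. The objections concern how much it matters.

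- **Nothing is lost.** Both series are still computed, each under the other's name. Within a series both arms get the same formula, so the between-arm comparison is a valid comparison of the other correction. This stands, and it makes the error recoverable. It does not make the tables right.
- **The use is descriptive.** No hypothesis test, efficacy endpoint, significance level or sample size uses QTc. The dosing modification criteria in protocol section 6.6 do not mention it, and the investigator's own ECG review in section 7.5.4 does not depend on the SAP derivation. This stands and limits the reach of the error to safety reporting.
- **Prolongation at slow rates is not hidden from the report as a whole.** It would still appear under the QTcB label. That is correct, but it would be understated in the table labelled QTcF.
- **The impact on outlier counts cannot be sized.** The SAP states no cut-offs, the documents give no heart-rate distribution, and QT itself varies with heart rate. This stands, so the millisecond figures are illustrations, not predictions.
- **A clash with machine-reported QTcB and QTcF is not established.** The documents do not say that device-corrected values enter the database or by which formula. Such a clash would arise only if they did and used the standard definitions.

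**Conclusion.** The concern holds. SAP 7.7.5 assigns each correction the other's exponent, and no other part of the documents corrects it. If the text is followed, every QTcB and QTcF summary, outlier count and listing would carry the wrong label. The numerical discrepancy is zero only at 60 bpm. At other rates it scales as (HR/60)^(1/6), which for an assumed QT of 400 ms runs from −11.3 ms at 50 bpm to +42.1 ms at 100 bpm in the value labelled QTcF.

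The conclusion rests on the standard definitions of the two named methods and on the derivation being programmed as written. It concerns descriptive ECG safety outputs only. Because those outputs would be factually wrong as specified, the text should be corrected and not left to the programmer's judgement.

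**What to change.** In SAP section 7.7.5, exchange the two exponents:

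- QTcB = QT × (Heart Rate/60)^(1/2)
- QTcF = QT × (Heart Rate/60)^(1/3)

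Then check the ECG derivation program against the corrected text before database lock. If any tables or listings have already been produced from the existing text, regenerate them. The cost is one line of SAP text and a check of one derivation step; no additional data are needed.

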1.1.2.2. Pathogenesis and Outcome

Cardiomyopathy in FAC occurs when insoluble TTR amyloid fibrils deposit in cardiac tissue causing heart wall thickening with diastolic and systolic dysfunction, conduction defects, and arrhythmias, leading to congestive heart failure and death. Neuropathy is uncommon in FAC.

While there is a paucity of longitudinal clinical data on FAC, a few published reports have shown that FAC patients have a significantly worse prognosis compared to other causes of heart failure, with rapid deterioration of functional capacity, including their ability to walk as measured by the 6-MWD, and quality of life (QOL) resulting in early mortality.

The median survival of V122I patients from time of diagnosis in two retrospective studies was 27⁸ to 41 months^{8,9} and in the prospective Transthyretin Amyloidosis Cardiac Study (TRACS) study median survival was 26 months.¹⁰

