1.1.2.3. Current Management and Unmet Medical Need

There are currently no approved treatment options for patients with FAC. Patients are largely managed with supportive care aimed at alleviation of heart failure symptoms, including restriction of salt intake, diuretics, pacemakers, and arrhythmia management. Heart transplantation has been used rarely, as many patients are too old to undergo the procedure. There is a high unmet need for novel therapeutics to treat FAC.

ALN-TTRSC (International Nonproprietary Name: revusiran) is currently being developed as an RNA interference (RNAi) therapeutic for patients with FAC.

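### ECG interval summaries and outlier counts are not split by pacing status, although pacing is recorded at each visit and paced patients can enrol

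*SAP*

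**What the plan says.** SAP 7.7.5 describes four ECG outputs that matter here.

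- **Categorical findings.** The assessments collected at each visit include pacing: "Overall categorical assessments including rhythm, electrical pacing present in ECG, ST or T-wave changes, A-V Block". They are tabulated: "Frequency (associated percentage) of each of the overall categorical assessments will be summarized as well by visit and treatment group".
- **Continuous parameters.** "Descriptive statistics will be used to summarize continuous parameters by visit and treatment group". These include PR, QRS and QT, plus the derived QTcB and QTcF.
- **Outlier counts.** "An outlier analysis will be performed to summarize the frequency (associated percentage) of abnormal values at post-baseline visits (scheduled or unscheduled". This is done "by treatment groups for the following parameters (QTc, QTcB, QTcF, PR, QRS and HR". No numerical limit for an abnormal value is given.
- **Listings.** ECG measurements, their changes from baseline and the investigator's interpretation are listed. All ECG values are listed separately for any patient whose overall interpretation is abnormal and clinically significant.

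Protocol 9.2.4 adds summaries of ECG intervals as actual values and as changes from baseline. SAP 6.2.2 says that safety analyses use observed data. Neither section mentions paced recordings, and nor does Protocol 7.5.4 on ECG acquisition.

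On the population, Protocol 1.1.2.2 describes amyloid deposition causing "diastolic and systolic dysfunction, conduction defects, and arrhythmias". Protocol 1.1.2.3 lists among supportive measures "restriction of salt intake, diuretics, pacemakers, and arrhythmia management".

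**The concern.** Two general facts about ECGs, not stated in the documents, drive the concern. Ventricular pacing widens QRS and thereby lengthens QT. The PR interval of a paced beat does not measure native atrioventricular conduction. A paced tracing therefore says little about a drug effect on conduction or repolarization.

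If paced and unpaced tracings share one table, two errors are possible. With similar pacing in both arms, paced tracings add the same block of flagged values to each arm and dilute a real difference. With unequal pacing, they produce a difference even when the drug does nothing to native intervals. Either could mislead someone reading the ECG safety tables of a trial in cardiac amyloidosis, where conduction is already of interest.

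**Working it through.** **Step 1. Can paced recordings enter the tables?**

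| Place | What it shows |
|---|---|
| Protocol 4.1, criterion 5 | A hospitalization for pacemaker placement can count towards the heart failure history |
| Protocol 4.2 | No exclusion criterion names pacemakers |
| Protocol 7.3.9.2 | Pacemakers are a contraindication to cardiac MRI only |
| Protocol 1.3 | One Phase 2 patient had a defibrillator inserted as an SAE. This does not establish pacing, but shows that devices are implanted during treatment |
| SAP 7.7.5, SAP 6.2.2, Protocol 9.2.4 | No exclusion, flag or separate display of intervals from paced tracings |

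Paced patients can be enrolled, patients may become paced on study, and no rule separates their intervals. The outlier count is not limited to values that are new since baseline, so a patient paced before entry contributes as well as one newly paced.

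**Step 2. How large could the effect be?** The documents give no figure to reproduce. The following is an illustration only.

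Assumptions: every paced tracing is flagged; a share *p* of the counted units in an arm is paced; the unpaced outlier rate is *r*. Then

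pooled rate = *p* + (1 − *p*) × *r*

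*Dilution.* Take assumed unpaced rates of 10% (revusiran) and 5% (placebo), a true ratio of 2.0, with the same *p* in both arms.

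| *p* | Revusiran | Placebo | Difference (points) | Ratio |
|---|---|---|---|---|
| 10% | 0.10 + 0.90 × 0.10 = 19.0% | 0.10 + 0.90 × 0.05 = 14.5% | 4.5 | 1.31 |
| 20% | 0.20 + 0.80 × 0.10 = 28.0% | 0.20 + 0.80 × 0.05 = 24.0% | 4.0 | 1.17 |
| 30% | 0.30 + 0.70 × 0.10 = 37.0% | 0.30 + 0.70 × 0.05 = 33.5% | 3.5 | 1.10 |

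The ratio suffers far more than the difference, which falls only from 5.0 points to between 4.5 and 3.5.

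*Imbalance.* Take *r* = 5% in both arms, so no drug effect on native intervals, with 20% paced on revusiran and 10% on placebo.

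- Revusiran: 0.20 + 0.80 × 0.05 = 24.0%
- Placebo: 0.10 + 0.90 × 0.05 = 14.5%

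The gap of 9.5 points comes from pacing alone. Reversing the imbalance reverses its sign.

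**Step 3. What would the split recover?** Among unpaced recordings the comparison returns to 10% vs 5% in the first case and 5% vs 5% in the second, provided that pacing is unrelated to what the interval would otherwise have been.

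**The case against.** The strongest reply is that most of what is needed to interpret the tables is already planned. A reader might infer that the SAP collects the pacing item and then ignores it. That is not so: pacing frequency is reported by visit and arm, so a marked imbalance would be visible, and the ECG listings would let someone trace device-driven values. This stands, and narrows the gap to the missing link between pacing and intervals and the missing count of patients newly paced.

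A reader might also infer that any patient given a pacemaker will be counted as a QTc or QRS outlier. The text does not fix that. Inclusion of paced tracings follows from silence, no limits are stated, and a table specification outside these documents could add a rule. Flagging is what one would expect for ventricular pacing under usual limits, no more. The pacing item as described also does not separate atrial from ventricular pacing.

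Randomization protects against a spurious difference when pacing is balanced. Unequal pacing could itself be a treatment effect, and for that reason simply dropping paced recordings would be a poor remedy: if the drug worsened conduction, the affected patients would leave the interval tables once paced.

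Finally, the stakes are low. The output is descriptive, and post-baseline ECGs are scheduled only at Months 6, 12 and 18 and at early termination (Protocol Table 1-1). No efficacy conclusion depends on them.

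What survives is that separating tracings from listings after unblinding is a weaker basis for a safety statement than a split specified beforehand.

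**Conclusion.** The gap is real and minor. As written, the plan pools paced and native intervals in the summaries, the changes from baseline and the outlier counts, in a population where pacing is foreseeable. The expected consequence is dilution of a true arm difference or, with unequal pacing, an apparent one.

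The size cannot be derived from the documents. The ratios of 1.31, 1.17 and 1.10 and the contrast of 24.0% vs 14.5% rest on assumed pacing shares, assumed unpaced outlier rates and the assumption that every paced tracing is flagged. For the same reason, the documents do not support a stated number of patients who would be misclassified, or a claim that the ECG safety conclusion will be wrong.

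**What to change.** In SAP 7.7.5:

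- Keep the all-recordings tables, which also preserves agreement with Protocol 9.2.4.
- Add the PR, QRS, QT, QTc and HR summaries, changes from baseline and outlier counts by pacing status: unpaced at both baseline and the visit, versus paced at either.
- Add the number and percentage of patients newly paced since baseline by arm, and list their intervals. New pacing arises after randomization and could be affected by treatment, so it must stay in view.

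The split uses an item already collected. The cost is a few extra tables and smaller numbers in the unpaced subset. That subset is defined partly by what happens after randomization, so it is not a clean randomized comparison and should be read beside the newly-paced table.

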7.7.6 Physical Examination

For each body system, the frequency (and associated percentage) of patients with a categorical result of (Normal, Abnormal – Not Clinically Significant, Abnormal – Clinically Significant) will be presented by treatment group and visit.

Physical examination results will be provided in a data listing. Abnormal, Clinically Significant findings will be presented in a separate listing.

7.7.7 Anti-Drug Antibodies (ADA)

A tabular summary of the ADA results at each visit will be generated. A patient listing of any subjects with a positive result will be generated.

Version: 1.0

Alnylam Protocol No. ALN-TTRSC-004

7.7.8 Exploratory Biomarkers

Exploratory biomarkers collected will be presented in a patient listing.

7.8 Interim Analysis

An unblinded interim analysis for futility may be conducted by the unblinded DMC statistician once approximately half the patients have completed the study. The Statistical Analysis Plan will be updated to address the futility criteria.

